#### 1.4 Rationale for the Study and its Purpose

Recovery from acute illness invariably takes time and is associated with increased risk of new acute illness, physical dependency and mortality (figure 1). Delayed or incomplete recovery is common and increases with the age of the patient and the duration and seriousness of the acute disease. Recovery time can vary between a few days in otherwise healthy subjects with influenza to months, years or never in elderly patients after major illness. During a typical episode of acute serious illness with hospitalization the patient will be treated as an inpatient during the initial recovery phase which will be followed by a prolonged period in a long-term care facility, rehabilitation institution or at home with home nursing. Younger patients may recover at home without additional care, but will often be unable to work, adding to the costs for society.

The cause of the need for extended time to recover has not been explored extensively in the scientific literature and is by some viewed as "self-explanatory" while others call for more research. Prompt and adequate treatment of the acute illness, supportive treatment with fluids and nutrition and early mobilization are key focus areas in every hospital that are known to improve patient outcome and shorten recovery time. To our knowledge, no "recovery-improvement drug" exists. We aim to include patients in ICU who are in this late stabile phase and administer NR or placebo from that point and onwards for 90 days. This is a completely novel approach to the recovery phase where NR may be seen as a "recovery-improvement pill".

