2.3 Sample size

Assuming the time of hospitalization after randomization follows a Weibull distribution with a scale parameter λ = 18 and shape parameter κ =2.2 (corresponding to a median of 15 and an IQR of 10 – 21), we need to include 58 patients: 18 in the placebo group, 10 in the 250 mg/day group, 10 in the 500 mg/day group, and 20 in the 1 g/day group) in order to reach approximately 80% power to show a significant dose-response in this study with a maximal reduction in time of hospitalization of 33%. This calculation is based on optimal designs in dose-finding studies according to the MCPMod methodology with three alternative dose-response curves: linear, e-max and exponential (Pinheiro et al., 2014).

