3.1 Confidence Intervals and P-values

All calculated *P*-values will be two-sided and compared to a 5% significance level. If a *P*-value is less than 0.05, the corresponding treatment group difference will be denoted as statistically significant. All efficacy estimates will be presented with two-sided 95% confidence intervals. The statistical approach to account for multiple testing of three doses versus placebo is the closed multiple test procedure (see Section 2.4). As there is only one primary null hypothesis setup to be tested in this trial, there will be no further adjustments for multiplicity.

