6.2 Secondary Continuous Outcomes (Change from Baseline)

Secondary continuous outcomes with change from baseline include grip strength at day 90 and grip strength at day 7. The analyses will be performed on the FAS.

Statistical Method for Steps 1-3

A linear mixed model will be fitted to the three measurements of grip strength (baseline, day 7, and day 90) in each step. The model will contain fixed effects for treatment (NR vs placebo), time point (day 7 vs baseline & day 90 vs baseline), and treatment x time point interaction and a random intercept. Based on the fitted model, we can estimate change from baseline to day 7 and change from baseline to day 90 in each group and the between-group difference in changes from baseline for both time points.

Presentation of Results

We will present the observed mean values and standard deviation for each group at each time point (baseline, day 7, and day 90). We also present the estimated change from baseline to day 7 and the estimated change from baseline to day 90 in each group with 95% confidence intervals, and the estimated between-group differences in changes from baseline to day 7 and to day 90 (the treatment difference), also with 95% confidence intervals.

Missing Data

Missing data on grip strength at either day 7 or day 90 will be handled by the linear mixed model, under the assumption of missing at random. There is no missing data on grip strength at baseline, so all patients will be included in the model.

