6.5 Assumption Checks and Alternative Analyses

Assumption checks will be performed for the primary and all secondary outcomes according to the statistical methods used to analyzed them.

Weibull and Cox Proportional Hazard Models

The Weibull and Cox proportional hazard regression models assumes that the hazard ratio is constant over time. This will be checked by plotting -log(log(survival)) curves for each treatment against log(analysis time) and assessing if the curves are parallel. If the proportional hazard assumption is deemed to be violated, alternative parametric survival models will be fitted instead. The following survival distributions will be considered: exponential, Gompertz, and lognormal. The goodness-of-fit of each model will be assessed with plots of Cox—Snell residuals against the estimated cumulative hazard function of the residuals, and the one with the best fit will be the chosen model.

Linear Mixed Models

For linear mixed models, we will compare observed and model-predicted outcomes. If we detect a poor-fitting model, we will refit the model with a log-transformation of the outcomes. We do not expect other model-fit problems, due to the simplicity of the model (only a random intercept and a few fixed effects); however, in the unlikely event that we will encounter numerical problems with fitting the model, we will remove the two time point variables and substitute it with a single (linear) variable for time.

Two-sample T test

The discrete numerical outcomes (number of new infections per patient and number of readmissions per patient) are limited to only a few possible values (with no great maximum), and as

such, there is no concern about the distribution of the outcomes, except for the situation where almost all patients have the same number and there is not enough variation in the data to get a meaningful result from the statistical methods. In that case, the outcome will be presented with the table of observed number and percentages in each treatment group in each category only.

7 Safety Analyses

General safety evaluations will be based on the incidence, intensity, and type of AEs, and clinically significant changes in the patient's physical examination findings, vital signs, clinical laboratory results and serum drug concentrations. Safety variables will be tabulated and presented for all patients in the safety set.

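### The grip-strength model gives the day-7 and day-90 changes one common variance; if the 90-day change varies more, its 95% interval will tend to be too narrow and the day-7 interval too wide

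*SAP*

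**What the plan says.** SAP 6.2: "A linear mixed model will be fitted to the three measurements of grip strength (baseline, day 7, and day 90) in each step". The fixed effects are treatment, time point and their interaction, and the only random term is the intercept ("treatment x time point interaction and a random intercept"). From this one fit the SAP takes "the between-group difference in changes from baseline for both time points". SAP 3.1 adds: "All efficacy estimates will be presented with two-sided 95% confidence intervals".

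SAP 6.5 describes the model again as having "only a random intercept and a few fixed effects". It plans a comparison of observed with model-predicted outcomes. The remedy for poor fit is a log-transformation; the remedy for numerical trouble is a single linear time term. Neither SAP section names another residual structure, an unstructured covariance or a robust standard error.

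SAP 2.4 reserves hypothesis tests for the primary outcome. For secondary outcomes it moves to the next lower dose only if the preceding 95% interval excludes the null value. Protocol 10.5.2 makes grip strength the secondary endpoint of special interest, and the outcome table in SAP section 5 lists it for the main article.

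**The concern.** A random intercept with independent, equal-variance residuals is compound symmetry: one variance at all three visits and one correlation between any two of them. The model therefore uses one variance for both changes, although one covers a week in hospital and the other about three months of recovery. SAP 2.7 lets the day-90 visit fall 30 days early to 90 days late, that is day 60 to day 180, which could add spread.

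If the true variances differ, the model averages them. The interval for the more variable change is then too short and the interval for the less variable change too long. At day 90 that would mean excluding zero more than 5% of the time when there is no effect, and so opening the route to the medium and low doses too readily. At day 7 it would mean wasted precision in arms of 10 to 20 patients. Neither remedy in SAP 6.5 relaxes the constraint.

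**Working it through.** **Inputs from the documents.** Three measurements per patient; random intercept only (SAP 6.2, 6.5); two-sided 95% intervals (SAP 3.1); group sizes "18 in the placebo group, 10 in the 250 mg/day group, 10 in the 500 mg/day group, and 20 in the 1 g/day group" (SAP 2.3). Step 1 therefore compares 20 with 18 (38 patients), and steps 2 and 3 each compare 10 with 18 (28 patients).

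**Inputs assumed.** The documents give no SD, correlation or change variance for grip strength, so there is no stated figure to reproduce. I assume an SD of 10 kg at each visit (12 kg at day 90 in one row) and a range of correlations. A common rescaling of the SDs does not alter the ratios below.

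**Algebra.** Let V7, V90 and V97 be the true variances of the baseline-to-7, baseline-to-90 and 7-to-90 differences. With SDs a and b and correlation r, V = a² + b² − 2rab. The model sets all three equal to 2σ², where σ² is the residual variance. With complete data, 2σ² estimates the mean M = (V7 + V90 + V97)/3. Then:

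- model SE / true SE = √(M/V);
- approximate coverage = 2Φ(1.96·√(M/V)) − 1;
- the day-90 interval is too narrow only if V90 > M, that is V90 > (V7 + V97)/2;
- the day-7 interval is too wide only if V7 < M, that is V7 < (V90 + V97)/2.

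**Worked case, 0.9/0.7/0.75.** V7 = 200(1 − 0.9) = 20; V90 = 200(1 − 0.7) = 60; V97 = 200(1 − 0.75) = 50; M = 130/3 = 43.3. The SE ratios are √(43.3/20) = 1.47 and √(43.3/60) = 0.85. For 20 v 18, 1/20 + 1/18 = 0.1056. The model SE is √(43.3 × 0.1056) = 2.14 kg at both visits. The true SEs are √(20 × 0.1056) = 1.45 kg at day 7 and √(60 × 0.1056) = 2.52 kg at day 90.

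| Assumed correlations (base-7 / base-90 / 7-90) | V7, V90, V97 | SE ratio day 7, day 90 | Coverage day 7, day 90 |
|---|---|---|---|
| 0.8/0.8/0.8 | 40, 40, 40 | 1.00, 1.00 | 95%, 95% |
| 0.9/0.7/0.75 | 20, 60, 50 | 1.47, 0.85 | 99.6%, 90.4% |
| 0.95/0.8/0.85 | 10, 40, 30 | 1.63, 0.82 | over 99%, 89% |
| 0.9/0.7/0.75, day-90 SD 12 | 20, 76, 64 | 1.63, 0.84 | 99.9%, 89.9% |
| 0.7/0.7/0.9 | 60, 60, 20 | 0.88, 0.88 | 91.6%, 91.6% |
| 0.8/0.75/0.6 | 40, 50, 80 | 1.19, 1.07 | 98.0%, 96.3% |
| 0.75/0.8/0.75 | 50, 40, 50 | 0.97, 1.08 | 94.2%, 96.6% |

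**Simulation checks.**

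- REML fits of the SAP model (20 v 18, 600 runs, complete data) at 0.9/0.7/0.75 gave mean SEs of 2.13 and 2.13 against empirical SDs of 1.41 and 2.44, with coverage 99.8% and 90.0%.
- 20,000 trials per scenario (20 v 18 and 10 v 18) at 0.9/0.7/0.75, 0.9/0.6/0.65 and 0.95/0.8/0.85 put day-90 coverage at about 88-90% and the day-7 SE at 1.45-1.68 times its true value. A t interval on the change score, which equals the unstructured analysis with complete data, covered about 95% throughout.
- With 20% of day-90 values missing, REML day-90 coverage was 86.2% at 0.9/0.7/0.75, against 93.0% when the random-intercept model was true.

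**How plausible is the harmful pattern?** Suppose recovery after day 7 is uncorrelated with recovery before it, and each visit adds independent noise of variance t. Let D7 and D be the between-patient variances of true change to day 7 and day 90. The squared day-90 SE ratio is (2D/3 + 2t)/(D + 2t), which is below 1 whenever D > 0. The day-7 interval is too wide whenever D7 < 2D/3. This is a model of recovery, not evidence from the trial; catch-up recovery (negatively correlated phases) could remove or reverse it.

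**The case against.** A reader might infer that the day-90 interval is certainly too narrow and the day-7 interval certainly too wide. The model does not imply that. Both inequalities above must hold, and no grip-strength figure in either document establishes them. The last three rows of the table give both too narrow, both too wide, and the reverse. This objection stands, and the point is conditional for that reason.

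A reader might also take Protocol 1.4 as showing that 90-day changes vary more: "Recovery time can vary between a few days in otherwise healthy subjects with influenza to months, years or never in elderly patients". That passage concerns recovery time across acute illness in general, not grip-strength variance among stable inpatients expected to stay at least another week. The protocol also expects its exclusion criteria to make participants more alike. It lends plausibility only.

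Two further overstatements should be avoided.

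- The two intervals have equal width only with complete data. With 20% of day-90 values missing at 0.9/0.7/0.75, the mean SEs were 2.05 at day 7 and 2.24 at day 90.
- The check in SAP 6.5 is not necessarily blind. Two arms by three visits is a saturated mean model, so with complete data the group means fit whatever the covariance; individual predictions, however, might show unequal spread. The firmer criticism is that neither listed remedy would correct it.

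Finally, the stakes are modest. SAP 2.4 treats all efficacy analyses other than the primary one as supportive or exploratory, the minimum-effective-dose decision does not use grip strength, and a day-7 interval that is too wide errs on the cautious side. All of this stands and limits the weight of the point. It does not remove the untested equal-variance assumption.

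**Conclusion.** The concern holds in conditional form. That the model imposes one variance on both changes is certain, given independent, equal-variance residuals, and the SAP names no other structure. The direction of any error is plausible but unproven. If the assumed decaying correlations are near the truth, a nominal 95% day-90 interval would exclude zero about 10-12% of the time under no effect. If compound symmetry holds, nothing is lost. The damage is confined to secondary estimates and to whether their lower-dose steps are carried out. It is worth correcting because the remedy is cheap and does not depend on which pattern is true.

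**What to change.** In SAP 6.2, replace the random intercept with an unstructured 3x3 within-patient covariance for baseline, day 7 and day 90, fitted by REML with Kenward-Roger degrees of freedom. The fixed effects and the reported contrasts can stay.

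In SAP 6.5, amend the description of the model as random-intercept only, and replace the linear-time remedy with a fallback for non-convergence that leaves the two change variances free. A separate comparison of change from baseline at each visit would do; the t test listed for frailty in Protocol 10.5.4, applied visit by visit, is of this kind. Heterogeneous compound symmetry should not be the fallback: it keeps one common correlation, so with equal SDs it gives V7 = V90 again.

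The cost is a few sentences and one model option in the planned software. Statistically, six covariance parameters are estimated instead of two, in samples of 28 to 38 patients. The per-visit fallback would use only patients measured at that visit, so it gives up some of the mixed model's handling of missing values and should remain a fallback.

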6.3 Secondary Time to Event Outcomes

All-cause mortality is the only secondary time to event outcome. The analysis will be performed on the FAS.

Statistical Method for Steps 1-3

In each step, a Cox proportional hazard regression model with treatment (NR vs placebo) as explanatory variable for the outcome will be fitted. The time at risk is defined in Section 5.

Presentation of Results

The estimated HR for treatment with a 95% confidence interval will be reported. A plot of the Kaplan-Meier survivor function (for time to all-cause mortality) of each dose and placebo will be presented.

Missing Data

There will be no missing data on mortality during the study's follow-up time.

6.4 Secondary Discrete Numerical Outcomes

The secondary discrete numerical outcomes are number of new infections per patient and number of re-admissions per patient. Both outcomes are measured as a count from 0 to the maximal number of events (new infections or re-admissions). We expect the maximal numbers of events to be at most 10. The analyses will be performed on the FAS.

Statistical Method for Steps 1-3

The mean number of events per patient will be compared between the NR and placebo groups – in each of the three steps – with a two-sample T test with adjustment for unequal variances (Fagerland et al., 2011).

Presentation of Results

The observed number and percentages in each treatment group in each category (0, 1, 2, ..., max number of events) will be presented together with the observed mean values and standard deviations in each treatment group and the estimated treatment difference with a 95% confidence interval.

Missing Data

If a patient has died, we will impute the missing data with the 80th percentile for the variable of interest (based on all patients regardless of treatment group). In cases where the 80th percentile= 0, the maximum number of events will be used.

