3.3 Estimands and Intercurrent Events

A composite variable strategy will be used to address intercurrent events (ICH E9(R1), 2019). In the B3SHORT trial, the relevant intercurrent event is death. Under the composite variable strategy, patients who die without a measurement of the outcome, and when death is informative of the outcome, will be given a value of the outcome variable that reflects that they are dead. This applies to some of the secondary outcomes. The precise definition of how this will be handled for each outcome will be given in Section 6 (Statistical Analysis Methods) under the Missing Data section.

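### SAP 6.4 does not say how infections and re-admissions recorded before death enter the imputed count, and sets no floor at them, so some patients who die can be scored below what was observed

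*SAP*

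**What the plan says.** SAP 3.3 adopts a composite variable strategy with death as the intercurrent event: "patients who die without a measurement of the outcome, and when death is informative of the outcome, will be given a value" that shows the patient is dead. It leaves the exact handling of each outcome to the Missing Data paragraphs of Section 6.

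For the two count outcomes, that paragraph in SAP 6.4 reads: "If a patient has died, we will impute the missing data with the 80th percentile for the variable of interest (based on all patients regardless"; the percentile is thus taken with the arms pooled. There is one exception: "In cases where the 80th percentile= 0, the maximum number of events will be used".

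SAP 5 defines both outcomes as a number per patient. Infections are added up from one contact to the next, re-admissions run to the end of the study, and the outcome table gives 65 weeks for both. SAP 6.4 adds: "We expect the maximal numbers of events to be at most 10". The analysis is an unequal-variance t test on the full analysis set: "The mean number of events per patient will be compared between the NR and placebo groups".

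Neither SAP 6.4 nor any other section says whether events recorded before death are kept, replaced or added to, and none sets a minimum at the recorded count.

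**The concern.** A patient who dies during the 65 weeks already has a partial count, even if it is 0. If the pooled percentile overwrites that count, two patients with the same recorded history can score differently, and the one who died can get the better score. With a percentile of 2, a patient with 4 re-admissions scores 4 if alive and 2 if dead. SAP 3.3 intends that a patient who dies "will be given a value of the outcome variable that reflects that they are dead"; a score below the recorded events does not do that.

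Both outcomes are among the three that SAP 5 lists as safety secondary endpoints, and both are for the main article. The groups are small (18 placebo; 10, 10 and 20 on NR), so a few rescored patients can move a mean visibly. SAP 2.4 also lets Steps 2 and 3 proceed for a secondary outcome only if the preceding interval excludes the null, so a shift in Step 1 can decide whether lower-dose estimates are produced.

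**Working it through.** **1. Is there a figure in the plan to reproduce?** No. The documents give no event rate, death rate or power for these outcomes. Rates below are assumptions; the rule and the group sizes come from the SAP.

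**2. Which reading is natural?** Three are possible.
- *Keep the partial count as it stands.* Nearly every patient who dies has one, so the imputation rule would apply to almost nobody.
- *Add the percentile to the partial count.* SAP 6.4 describes a scale from 0 to the maximum number of events. Adding the fallback maximum to a non-zero partial count would leave that scale. SAP 3.3 also speaks of a value of the outcome, not an increment.
- *Replace the total.* This fits both sections best, but it is inferred, not stated.

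**3. The rule under replacement.** Let x be the count recorded before death and P80 the 80th percentile of all 58 recorded counts.
- If P80 = 0, the score is the maximum, so score ≥ x for everyone.
- If P80 ≥ 1, the score is P80, and every patient who died with x > P80 is lowered by x − P80.

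**4. Illustration.** Assume 58 counts: 30 × 0, 14 × 1, 8 × 2, 3 × 3, 2 × 4, 1 × 6. The total is 14 + 16 + 9 + 8 + 6 = 53 and the mean is 53/58 = 0.91. The 80th percentile sits at ordered position 1 + 0.8 × 57 = 46.6. Positions 45 to 52 are all 2, so P80 = 2. A patient who died with 3, 4 or 6 events is lowered to 2; one who died with 0 or 1 is raised to 2.

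**5. Effect on a group mean.** Lowering one patient by k events moves the mean by k/20 in the normal-dose group, k/18 on placebo and k/10 in the other two groups. Two normal-dose patients lowered from 4 to 2 move that mean by (2 + 2)/20 = 0.20.

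**6. How often, under assumed rates.** Simulated trials of 58 patients, death times uniform over follow-up, P80 taken from the recorded counts, SAP fallback applied. Overdispersion is gamma frailty (variance 0.7 to 1.5), except that the last two rows use Poisson or gamma-Poisson (shape 1) counts.

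| Mean events | Deaths | Death risk linked to frailty | Deaths lowered | Trials with at least one lowered |
|---|---|---|---|---|
| 0.8 to 2.0 | 10% to 20% | yes | about 9% to 27% | about 40% to 98% |
| 0.8 to 2.0 | 10% to 20% | no | about 6% to 8% | about 29% to 63% |
| 0.3 | 10% to 20% | either | about 2% to 6% | about 11% to 33% |
| 0.3 to 2.0 | 10% or 30% | no | 2% to 8% | 10% to 77% |
| 0.15 | 10% or 30% | no | 0.2% to 0.5% | 1% to 2% |

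At mean 0.15 the percentile is 0 in 92% to 97% of trials, so lowering is rarely possible.

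**7. The other tail.** In the first row, about 55% to 83% of deaths are raised and the mean net change per death is upward, about +0.2 to +1.8 events.

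**8. With a floor.** If the score is max(x, imputed value), then score ≥ x always, so 0% of deaths are lowered in any scenario. A patient who died with 6 recorded events keeps 6. Patients below the imputed value are still raised as the SAP intends.

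**The case against.** The strongest reply is that replacement is not what the SAP says. It imputes missing data, and SAP 3.3 confines the strategy to patients who die without a measurement. A recorded partial count might be such a measurement, or only the unobserved remainder might be imputed. This stands to the extent that replacement is an inference. It does not remove the point: SAP 3.3 hands the precise definition to Section 6, SAP 6.4 does not supply it, and the same clause settles the matter on any reading.

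A reader might go further and infer that the rule generally pulls a harmful arm towards no difference. The documents do not support that. Two NR deaths with 4 events each and a percentile of 2 lower the NR mean by 0.20, but two NR deaths with 0 events raise it by the same (2 + 2)/20 = 0.20. In the simulated scenarios the average change per death was upward, so the arm with more deaths tends to gain events.

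A reader might also infer that recorded events vanish from the report. They do not: SAP 6.4 already presents observed counts by category with observed means and standard deviations, and mortality is analysed separately in SAP 6.3. The comparison itself, however, would use the rescored counts.

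Finally, these outcomes are estimated, not tested, and SAP 2.4 calls every analysis other than the primary supportive or exploratory. That limits the weight of the point.

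**Conclusion.** The point holds as a gap in a stated rule. SAP 6.4 does not say how events before death enter the imputed count and sets no floor. If the percentile replaces the count and is 1 or more, a patient who died with more events than the percentile is scored below the recorded count and below a survivor with the same history, contrary to SAP 3.3. If the percentile is 0, this cannot happen.

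The size depends on rates that the documents do not give. For assumed means of 0.3 to 2.0 events and 10% to 20% deaths, about 2% to 27% of deaths would be lowered; the upper part of that range needs overdispersed counts and a death risk that rises with frailty. Most deaths are raised, so the finding is one of mis-scored individuals and not of bias in a known direction. The primary analysis is untouched.

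**What to change.** Add one clause to the Missing Data paragraph of SAP 6.4: *a patient who dies before week 65 is given the larger of (a) the number of events observed up to death and (b) the imputed value; this applies to new infections and to re-admissions.*

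This states how the partial count is used, keeps the SAP's percentile and its fallback to the maximum, and ensures that no death lowers a score. The cost is one clause and one line of code. No new data are needed, and the planned presentation of observed counts and means can stay as it is.

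### The death imputation for infection and re-admission counts jumps from about 1 to the maximum at one threshold, so a single patient's event can change the sign of a difference or the decision to continue to the next dose

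*SAP*

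**What the plan says.** SAP 6.4 covers two outcomes, new infections per patient and re-admissions per patient. Its rule for deaths is: "If a patient has died, we will impute the missing data with the 80th percentile for the variable of interest", where the percentile is "based on all patients regardless of treatment group". It then adds: "In cases where the 80th percentile= 0, the maximum number of events will be used". On the size of that maximum it says only: "We expect the maximal numbers of events to be at most 10".

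The arms are compared "with a two-sample T test with adjustment for unequal variances", and a mean difference with its 95% interval is reported. The group sizes in SAP 2.3 are "18 in the placebo group, 10 in the 250 mg/day group, 10 in the 500 mg/day group, and 20 in the 1 g/day group". Under SAP 2.4 secondary outcomes are estimated and not tested, but the interval still acts as a gate: the medium dose is compared with placebo only if the normal-dose interval excludes zero, and the low dose only if the medium-dose interval does.

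The SAP leaves three things open: whether the maximum is the largest observed count or the expected ceiling of 10, whether the percentile includes the patients who died, and whether events recorded before death are kept. It lists no sensitivity analysis for this imputation.

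**The concern.** A rule that scores death as a bad outcome should not score it much worse because one fewer patient had an infection. Here it does, at one point. While the pooled 80th percentile is 1, a death counts as 1. When it drops to 0, a death counts as the maximum.

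The percentile is pooled over all four groups, so the switch can be set by a patient who is not in the comparison being made. With 10 to 20 patients per NR group and 18 on placebo, a few deaths moved from 1 to the maximum can outweigh the observed events in the mean difference and inflate its variance. At stake are the direction of the reported difference and whether the lower doses are estimated at all.

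**Working it through.** **No figure to reproduce.** SAP 6.4 states no numerical result. The 80% power in SAP 2.3 concerns the primary outcome and does not enter here.

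**Inputs from the SAP.** Groups of 18, 10, 10 and 20 (58 in total); the imputation rule; Welch 95% intervals; the gate in SAP 2.4. **Assumed:** the number and split of deaths, the event counts, and that the maximum is the largest observed count.

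**1. Where the switch lies.** Take the 80th percentile as the ordered value at position 0.8 × n, rounded up.
- n = 54: 43.2, so the 44th value. It is 0 if at least 44 patients have no event, that is, if at most 10 have any. With 11 it is 1.
- n = 58: 46.4, so the 47th value. It is 0 with at most 11 patients with events, and 1 with 12.
- n = 53: the split is 10 versus 11. n = 56: 11 versus 12.

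An interpolating definition puts the threshold in the same place but can give a fraction. For n = 54 with 11 patients having one event each, the position is 1 + 0.8 × 53 = 43.4 and the value is 0.4. The jump is then larger.

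**2. Size of the jump.** Suppose 3 of 18 placebo and 1 of 20 normal-dose patients die, each scored m. The imputed part of placebo minus normal dose is 3m/18 − m/20:
- m = 1: 0.167 − 0.050 = 0.12
- m = 3: 0.50 − 0.15 = 0.35
- m = 6: 1.00 − 0.30 = 0.70

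**3. A change of sign.** Five deaths, 4 on 1 g and 1 on placebo. Survivors with events: placebo 6 of 17 (one each), 1 g 1 of 16 (one), low dose 2 of 10 (one each), medium dose 1 of 10 (three events).
- 10 of 53 have events, the percentile is 0 and deaths score 3. 1 g: (1 + 4 × 3)/20 = 0.650. Placebo: (6 + 3)/18 = 0.500. Difference +0.150 (95% CI −0.523 to 0.823).
- One more low-dose patient has one event: 11 of 53, and deaths score 1. 1 g: (1 + 4)/20 = 0.250. Placebo: (6 + 1)/18 = 0.389. Difference −0.139 (−0.453 to 0.175).

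The observed data in the two compared arms are identical in both cases.

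**4. A change in the gate.** Two deaths on 1 g and none on placebo; 7 of 18 placebo patients with one event; no events in 1 g survivors; one patient with five events in another dose group.
- 12 of 56 with events, deaths score 1: 2/20 − 7/18 = −0.289 (−0.569 to −0.008). Step 2 is done.
- 11 of 56, because one patient fewer in the other dose groups has an event; deaths score 5: 10/20 − 7/18 = +0.111 (−0.641 to 0.863). Step 2 is not done.

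**5. How often the switch is triggered.** Negative binomial counts in 54 patients, dispersion 0.5. The range covers two readings of that parameter: size 0.5, and variance μ + 0.5μ².

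| Mean count | Trials with 80th percentile = 0 |
|---|---|
| 0.1 | about 99% |
| 0.2 | 67–79% |
| 0.3 | 19–41% |
| 0.5 | 0–5% |

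At mean 0.3 (size 0.5), the average maximum in triggered trials is about 2.8, and a maximum of 6 or more occurs in about 3% of them. With 10% deaths, 16–26% of trials at means 0.2 to 0.4 lie within one patient of the switch, and the step 1 sign flips in about 3–4% of all trials.

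**6. Shape of the penalty.** In the same simulation the average imputed value is 1.5, 2.0, 1.8, 1.4, 1.2 and 1.8 at mean counts 0.1, 0.2, 0.3, 0.4, 0.6 and 1.0. It rises and falls. At mean 0.3 it averages 2.8 when the percentile is 0 and 1.0 when it is not.

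**The case against.** Four points on the other side carry weight.

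- Scoring deaths badly is the declared composite strategy (SAP 3.3), and the switch presumably exists so that a death is never scored 0. That purpose is sound, but a floor of 1 meets it without a jump.
- These are supportive outcomes. SAP 2.4 excludes hypothesis tests on them, SAP 6.4 reports observed counts by category beside the estimate, and mortality is analysed separately. This limits the damage. It does not repair the estimate or the gate.
- SAP 6.5 falls back to a table alone when almost all patients have the same count. That does not describe about 19% of patients with events, which is where the switch lies.
- The event rate is unknown. Infections include mild ones, re-admissions are all-cause, and both run to 65 weeks. At a mean of 0.5 or above the switch would seldom or never be triggered.

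A reader might infer that rarer events always bring a heavier penalty. They do not: below the switch, rarer events also lower the observed maximum, and if nobody has more than one event there is no jump. A reader might also infer that one event could turn a significant benefit into significant harm. No such case appeared in 10,560 configurations examined, and both intervals in the sign-change example include zero. Nor is 10 a working value for the maximum: the SAP gives it as a ceiling.

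**Conclusion.** The rule as written has a local discontinuity that runs the wrong way, and this follows from the text alone. Its consequences are conditional. They need at least one death, usually unbalanced between arms, a maximum above 1, and a proportion of patients with events near 20%. Under those conditions one event can change the sign of the step 1 estimate, or whether steps 2 and 3 are done.

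The documents supply no death or event rates, so the shifts from 0.12 to 0.35 or 0.70 events per patient and the trigger rates are illustrations, not forecasts. The documents do not support saying that the imputation, and not the observed events, sets the result in general: with few or balanced deaths the effect is small. The primary analysis is untouched. The change is worth making because the defect lies in a stated rule and is cheap to remove.

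**What to change.** In SAP 6.4, delete the switch and use one monotone floored rule for both counts. For example, a patient who died receives the largest of the pooled 80th percentile, 1, and the patient's own count up to death. State which patients enter the percentile and how it is computed. Keep maximum-value imputation only as a labelled sensitivity analysis, with the maximum defined; SAP 6.1 already places it there for the primary outcome.

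In the sign-change example, using the larger of the 80th percentile and 1 gives −0.139 (−0.453 to 0.175) both before and after the extra event, so the jump is gone.

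The cost is about two sentences and no data. Protocol 10.4 allows amendments to the plan until database lock. The downside is that the floor of 1 is a convention, and deaths are penalised less when events are rare than under the present rule.
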